# **SYNOPSIS**

TITLE	Randomised multi-arm trial of ruxolitinib (RUX) and fostamatinib (FOS) for COVID-19 pneumonia		
AIM	To evaluate efficacy of RUX and FOS compared to standard of care (SOC) in the treatment of COVID-19 pneumonia		
PRIMARY OBJECTIVE	To determine the efficacy of RUX and FOS compared to standard of care (SOC) to reduce the proportion of hospitalised patients progressing from mild or moderate to severe COVID-19 pneumonia		
SECONDARY OBJECTIVES	
 
Determine the efficacy of RUX or FOS to reduce mortality
 
Determine the efficacy of RUX or FOS to reduce the need for invasive ventilation or ECMO
 
Determine the efficacy of RUX or FOS to reduce the need for non-invasive ventilation
 
Determine the efficacy of RUX or FOS to reduce the proportion of patients suffering significant oxygen desaturation
 
Determine the efficacy of RUX or FOS to reduce the need for renal replacement therapy
 
Determine the efficacy of RUX and FOS to reduce the incidence of venous thromboembolism COVID-19 pneumonia
 
Determine the efficacy of RUX and FOS to reduce the severity on COVID-19 pneumonia [graded by a modified WHO Ordinal Scale]
 
Determine the efficacy of RUX or FOS to reduce the level of inflammatory biomarkers
 
Determine the efficacy of RUX or FOS to reduce blood ferritin, CRP, LDH, and D-dimer
 
Determine the efficacy of RUX or FOS to reduce the level of serum creatinine
 
Determine the efficacy of RUX or FOS to reduce duration of hospital admission
 
Evaluate the safety of RUX and FOS for COVID-19 pneumonia
 
Determine the impact of RUX or FOS to reduce the development of the post-acute COVID-19 syndrome in patients who presented with mild-moderate COVID-19 pneumonia
 
Assess impact of signal inhibitors (RUX or FOS) on health related quality of life at 6, 12 and 18 months post COVID-19
 
		
DESIGN	Multi-site, Two stage, open label, randomized (1:1:1) controlled trial		
STUDY DURATION	Treatment is for 14 day from baseline. Patients will receive follow-up assessment at 7, 14 and 28 days after the first study dose.  Screen Period: up to 7 days		
	Treatment Period: 14 days		
	1.000.00.1.00.2.00.0		

MATIS version 4.0 dated 2nd November 2022

IRAS: 282552 Page **14** of **57** 

[figure not shown]

	T
	Follow-up period: Day 14 to 28
	Follow-up period of sub-study: Up to 24 months

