SAMPLE SIZE	171 in Stage 1 (57 per arm) and up to an additional 285 in Stage 2 (additional 95 per included arm), to allow for 5% dropout. Patients with mild or moderate COVID-19 pneumonia will be recruited. Patients will be enrolled into RUX, FOS or SOC groups, as shown in the flow chart.
STUDY SITES	The opening site will be Imperial College Healthcare NHS Trust in the United Kingdom. Additional UK based sites for the trial will include Reading, London North West University Healthcare NHS Trust (Northwick Park Hospital and Ealing Hospital, Leeds and Sheffield Teaching Hospitals NHS Foundation Trust.
INCLUSION CRITERIA	
 
Patients age ≥ 18 years at screening
 
Patients with mild or moderate C19 pneumonia, defined as Grade 3 or 4 severity by the WHO COVID-19 Ordinal Scale
 
Patients meeting criteria:         
 
Hospitalization AND
 
SARS-CoV2 infection (clinically suspected* or laboratory confirmed) AND
 
Radiological change consistent with COVID-19 disease
 
 
 
CRP ≥ 30mg/L at any time point
 
Informed consent from patient or personal or professional representative
 
Agreement to abstain from sexual intercourse or use contraception that is >99% effective for all participants of childbearing potential for 42 days after the last dose of study drug. For male participants, agreement to abstain from sperm donation for 42 days after the last dose of study drug.
 
Non-English speakers will be able to join the study. If patients are unable to understand verbal or written information in English - hospital translation services will be requested at the participating site for the participant where possible.
 

	Patients normally on non-invasive ventilation such as continuous positive airway pressure (CPAP) at home are eligible
EXCLUSION CRITERIA	
 
Requiring either invasive or non-invasive ventilation including CPAP or high flow nasal oxygen at any point after hospital admission and before baseline not due to a pre-existing condition (e.g. obstructive sleep apnoea)
 
Grade ≥ 5 severity on the modified WHO COVID-19 Ordinal Scale, viz. O2 saturation < 90% on ≥ 60% inspired oxygen at baseline; non-invasive
 

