#### 5.2 INCLUSION CRITERIA

- Patients age ≥ 18 years at screening
- Patients meeting criteria of:
  - Hospitalization AND
  - SARS-CoV2 infection (clinically suspected\* or laboratory confirmed) AND
  - o Radiological change consistent with COVID-19 disease
- Mild or moderate (Grade 3 or 4 severity by modified WHO COVID-19 Ordinal Scale) C19 pneumonia
- CRP ≥ 30mg/L at any time point
- Informed consent from patient or personal or professional representative
- No medical history that might, in the opinion of the responsible clinician, put the patient at significant risk if he/she were to participate in the trial
- Agreement to abstain from sexual intercourse or use contraception that is >99% effective for all participants of childbearing potential for 42 days†
- For male participants, agreement to abstain from sperm donation for 42 days after the last dose of study drug ‡
- Non-English speakers will be able to join the study. If patients are unable to understand verbal or written information in English - hospital translation services will be requested at the participating site for the participant where possible
- Patients normally on non-invasive ventilation such as continuous positive airway pressure (CPAP) at home are eligible

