#### 5.3 EXCLUSION CRITERIA

• Requiring either invasive or non-invasive ventilation including CPAP or high flow nasal oxygen at any point

MATIS version 4.0 dated 2nd November 2022

IRAS: 282552 Page **30** of **57** 

\* Clinical suspicion of COVID-19 pneumonia will be confirmed by two independent clinicians.

<sup>† Females must be either post-menopausal for at least 1 year or surgically sterile; or if female of child-bearing potential, must not be pregnant or lactating and must agree to use an acceptable method of birth control throughout the duration of the trial and for 30 days following the last dose. Acceptable methods of birth control are defined as: hormonal contraception (pill, injection or implant) used consistently for at least 30 days prior to enrolment, intrauterine device (IUD), double-barrier (ie, condom and spermicide, or condom and diaphragm), or true abstinence (when this is in line with the preferred and usual lifestyle of the subject).

<sup>‡ Male subject with a partner of childbearing potential must agree to use an appropriate double-barrier method of contraception during the time interval between administration of the first dose of study drug and 30 days following the last dose, or must agree to true abstinence (when this is in line with the preferred and usual lifestyle of the subject).

after hospital admission and before baseline not related to a pre-existing condition (e.g. obstructive sleep apnoea)

- Grade ≥ 5 severity on the WHO COVID-19 Ordinal Scale
- O₂ saturation < 90% on ≥ 60% inspired oxygen at baseline

- In the opinion of the investigator, progression to death is inevitable within the next 24 hours, irrespective of the provision of therapy
- Any medical condition or concomitant medication that in the opinion of the investigator would compromise subjects' safety or compliance with study procedures.
- Any medical condition which in the opinion of the principal investigator would compromise the scientific integrity of the study
- Known severe allergic reactions to the investigational agents
- Use of drugs within the preceding 14 days that are known to interact with any study treatment (FOS or RUX), as listed in the Summary of Product Characteristics
- Child Pugh B or C grade hepatic dysfunction
- Pregnant or breast feeding

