#### 7.16 TREATMENT DURATION

The planned duration of treatment is 14 days. Participants may be discontinued from treatment earlier due to unacceptable toxicity or disease progression which will be recorded as Serious Adverse Event (SAE). If participant is being discharged prior to day 14 they will go home and continue with the treatment plan.

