**Table 7. Schedule of events** 

	Screening	Baseline				Last visit
Study Day	-6 to 0	0	1 *	7 #	14#	28#
Time window		- 2 days	+ 1 day	± 3 days	± 3 days	± 3 days
Informed consent	х					
Inclusion/Exclusion criteria	х	Х				
Demographic data	х					
Medical history including major comorbidities	х					
Physical exam	х					
COVID-19 diagnosis, duration and severity	х					
Pregnancy test	х					
Vital signs	х	Х	Х	Х	Х	Х
NEWS score	х	Х	Х	Х	х	Х
Inflammatory markers (CRP, D-dimer, LDH, ferritin, full blood count)		х	Х	х	х	Х
PK levels*					х	Х
Full blood count ¶ (FBC)		Daily while on CYP3A4 inhibitor				
Coagulation, Chemistry, Ferritin, Troponin, Procalcitonin	х	х	x	x	х	х
FiO 2	х	Х	Х	х	х	Х
SpO₂ and/or PaO₂	х	Х	х	х	х	Х
Randomisation		Х				
Weight and Estimated height		Х				
Safety monitoring of liver and renal function	х	Х	Х	Х	х	Х
Length of stay						
Serious Adverse Events	х	Х	Х	х	х	х
Concomitant medications	Х	Х	Х	х	Х	Х
Serum		х		х	Х	х
Plasma		Х		х	Х	Х
RNA in PAXgene tube		Х		Х	Х	Х
PBMC		x		х	х	Х

<sup>+ data that is routinely collected for clinical purposes will be recorded and a visit is not required

<sup># in the event that the patient recovers from COVID19 and is discharged, these visits will not be mandated. Instead a visit should occur on the date of discharge. Where possible, patients will be contacted by telephone at day 7, 14 and 28 and invited to attend for blood tests to monitor resolution of illness.

\*Ruxolitinib dose for these patients will be assessed after 10 dialysis patients complete Day 14 through pharmacokinetics (PK) levels which will be assessed.

<sup>¶For patients randomized to ruxolitinib and prescribed a strong CYP3A4 inhibitor or dual CYP3A4/CYP2C9 inhibitor. Please refer to Section 7.8 for details.

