1.3 Study population

1.3.1 Eligibility criteria

Inclusion criteria

- Patients age ≥ 18 years at screening.
- Patients meeting criteria of:
 - o Hospitalization AND
 - o SARS-CoV2 infection (clinically suspected¹ or laboratory confirmed) AND
 - o Radiological change consistent with COVID-19 disease
- Mild or moderate (Grade 3 or 4 severity by modified WHO COVID-19 Ordinal Scale) C19 pneumonia.
- $CRP \ge 30 \text{mg/L}$ at any time point.
- Informed consent from patient or personal or professional representative.
- No medical history that might, in the opinion of the responsible clinician, put the patient at significant risk if he/she were to participate in the trial.
- Agreement to abstain from sexual intercourse or use contraception that is >99% effective for all participants of childbearing potential for 42 days.²
- For male participants, agreement to abstain from sperm donation for 42 days after the last dose of study drug.³
- Non-English speakers will be able to join the study. If patients are unable to understand verbal
 or written information in English hospital translation services will be requested at the
 participating site for the participant where possible.
- Patients normally on non-invasive ventilation such as continuous positive airway pressure (CPAP) at home are eligible.

¹ Clinical suspicion of COVID-19 pneumonia will be confirmed by two independent clinicians.

² Females must be either post-menopausal for at least 1 year or surgically sterile; or if female of child-bearing potential, must not be pregnant or lactating and must agree to use an acceptable method of birth control throughout the duration of the trial and for 30 days following the last dose. Acceptable methods of birth control are defined as: hormonal contraception (pill, injection or implant) used consistently for at least 30 days prior to enrollment, intrauterine device (IUD), double-barrier (ie, condom and spermicide, or condom and diaphragm), or true abstinence (when this is in line with the preferred and usual lifestyle of the subject).

³ Male subject with a partner of childbearing potential must agree to use an appropriate double-barrier method of contraception during the time interval between administration of the first dose of study drug and 30 days following the last dose, or must agree to true abstinence (when this is in line with the preferred and usual lifestyle of the subject).

Exclusion criteria

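### The contraception rule for women of childbearing potential ends 30 days after the last dose in one place and 42 days after it in another

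*Protocol*

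**What the plan says.** The requirement appears in four places.

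- **Protocol synopsis, inclusion criteria.** Abstinence or highly effective contraception is required "for all participants of childbearing potential for 42 days after the last dose of study drug".
- **Protocol 5.2, inclusion bullet.** The same criterion reads "use contraception that is >99% effective for all participants of childbearing potential for 42 days" and stops there, with no event from which the 42 days are counted. The bullet carries a dagger.
- **Dagger footnote (printed under 5.3).** A woman of childbearing potential "must agree to use an acceptable method of birth control throughout the duration of the trial and for 30 days following the last dose". The footnote also lists the acceptable methods.
- **SAP 1.3.1, footnote 2.** The same wording is repeated: "agree to use an acceptable method of birth control throughout the duration of the trial and for 30 days following the last dose". The SAP also repeats the 5.2 bullet without a starting point.

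The timeline comes from three other places. Protocol 7.16 says "The planned duration of treatment is 14 days". The study duration row of the synopsis gives "Follow-up period: Day 14 to 28" for the main study. Table 7 allows 3 days either side of the day 28 visit. For discharged patients the table's footnote drops the mandatory visits and substitutes calls: "Where possible, patients will be contacted by telephone at day 7, 14 and 28". The row "Pregnancy test" is marked at screening only.

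**The concern.** A woman must agree to this condition before she enters the trial, and the current text gives it two lengths. The shorter one sits in the most detailed text, which says who is covered, which methods count and for how long. Staff who read 5.2 with its footnote find a single post-dose figure for women, 30 days. The bullet's own 42 days does not correct that figure, because it is tied to no starting point.

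The Protocol itself gives reasons for care. Its section on crushing tablets (under 7.4) says fostamatinib can harm a fetus, and 11.1 lists developmental toxicity among the identified and potential risks of ruxolitinib. The days in dispute all fall after the last scheduled main-study visit and the last planned telephone contact, with no pregnancy test scheduled after screening. No later main-study contact is planned at which a woman told the shorter period could be corrected, so the wording agreed at entry has to be right.

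**Working it through.** The plan states no calendar end day for contraception, so there is no figure to reproduce. The check is date arithmetic.

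**Inputs**

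- Last planned dose: day 14 (Protocol 7.16).
- End of main-study follow-up: day 28 (synopsis), at the latest day 28 + 3 = day 31 (Table 7 window).
- Post-dose period: 42 days (synopsis) or 30 days (dagger footnote).

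**Formulas**, with *d* the day of the last dose

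- Synopsis end = *d* + 42.
- Footnote end = the later of the end of follow-up and *d* + 30, that is max(31, *d* + 30).
- Disputed days = *d* + 31 to *d* + 42.

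**Full course (*d* = 14)**

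- Footnote end = max(31, 14 + 30) = day 44.
- Synopsis end = 14 + 42 = day 56.
- Gap = 56 − 44 = 12 days.

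**Early stopping**

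| Last dose day | Footnote end | Synopsis end | Gap | Disputed days |
|---|---|---|---|---|
| 1 | 31 | 43 | 12 | 32 to 43 |
| 7 | 37 | 49 | 12 | 38 to 49 |
| 14 | 44 | 56 | 12 | 45 to 56 |

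For every *d* from 1 to 14, *d* + 30 is at least 31, so the 30-day limb always sets the footnote's end date. The gap is therefore (*d* + 42) − (*d* + 30) = 12 days throughout, and the disputed days always lie after day 31. On the full course the latest possible last visit falls 44 − 31 = 13 days before the footnote end and 56 − 31 = 25 days before the synopsis end.

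**Other readings**

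- *The 5.2 bullet.* If its 42 days run from the last dose, it agrees with the synopsis at day 56. If they run from baseline at day 0 (an assumption), it ends on day 42. That is 44 − 42 = 2 days before the footnote and 56 − 42 = 14 days before the synopsis.
- *The length of the trial.* The synopsis allows sub-study follow-up to 24 months, and Protocol 9.6 puts the end of the study about 10 years after the last enrolment. If the footnote meant either of these, it would run well past day 56 and be the longer of the two.

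**The case against.** The strongest reply is that the two texts are minimum periods and do not exclude each other. Contraception to 42 days after the last dose meets the synopsis and, on the main-study reading, the bullet and footnote as well. That is correct, and it makes the defect an ambiguous minimum rather than two requirements that cannot both be met. But no text tells a site to take the longer period, and a site working from the footnote alone would stop at 30 days.

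Second, day 44 assumes that the trial means main-study follow-up. The phrase is undefined, so the assumption has to be stated. The wider readings are implausible for a 14-day drug course, and they would still disagree with the synopsis. The 30 versus 42 day difference in post-dose wording does not depend on this point.

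Third, harm is not demonstrated. Nothing in the documents shows that 30 days is too short, the number of women affected is not given, and the patient information sheet is not in the file and may state one clear period. Protocol 11.4 also requires reports of drug exposure during pregnancy to be collected. All of this stands and keeps the severity low. Collecting such reports does not settle how long contraception should last, and a correct information sheet would not make the Protocol consistent.

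Finally, the SAP list is a copy taken from an earlier protocol version and governs no instruction to participants. It adds no independent evidence. Correcting it is housekeeping.

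**Conclusion.** The inconsistency is real and sits in current text. For women of childbearing potential, the synopsis and the dagger footnote to 5.2 differ by 12 days after the last dose: day 44 against day 56 on the full course, and the same gap for any last dose from day 1 to day 14. The calendar days rest on reading the trial as main-study follow-up to day 28, plus at most 3 days. No document supplied reconciles the two figures; the consent material could not be checked. Only women of childbearing potential who receive ruxolitinib or fostamatinib are affected. The severity is low: this is a safety instruction that is wrong as written, with no bearing on the statistical design and no evidence that anyone was put at risk.

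**What to change.** In the 5.2 bullet, the dagger footnote and the SAP 1.3.1 copies, replace both the open-ended 42 days and the 30-day clause with one period: *from the first dose of study drug until 42 days after the last dose*. This supplies the missing starting point, keeps explicit cover during treatment, and brings all the texts to day 56 on the full course (14 + 42), so the gap is 0. The documents give no basis for either figure; 42 days is proposed because it is the sponsor's own longer one.

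Check that the patient information sheet gives the same period. In the same pass, look at the adjacent double-dagger footnote, which sets 30 days for barrier contraception by men beside a 42-day limit on sperm donation. These are different obligations, so the difference may be intended, but it should be confirmed.

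The cost is wording only, with no effect on endpoints, alpha, power or sample size.

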#### 6 RANDOMISATION AND ENROLMENT

#### 6.1 ENROLMENT PROCEDURES FOR PATIENTS

Eligible patients who have given informed consent to participate will be enrolled to the study. With due consideration to the circumstances of possible admission to a high-level isolation unit a full study information sheet will be given subsequent to the consent discussion. All patients will have clinical information collected either directly through examination including a review of medical, contact and travel history, or from available medical notes. Information will be recorded in the case report form.

#### 6.2 RANDOMISATION

Patients will be randomized to one of three actively recruiting trial arms, RUX, FOS or SOC. Eligible patients will be allocated using a central web-based randomisation service that uses randomisation sequences with random block sizes that are stratified by age (<65 vs ≥65) and site. If stage 2 occurs with one intervention arm stopped then the randomisation ratio will be 1:1.

#### 6.3 UNBLINDING

Analysis will be undertaken primarily by the trial statistician who will be blinded to treatment assignment. Any analysis of primary efficacy outcomes or data with the potential to unblind the trial statistician (e.g. adherence to allocated intervention) will be undertaken by an independent statistician from Newcastle University. An independent statistician based in Imperial Clinical Trials Unit will hold the information to unblind the data for closed DMC discussions.

#### 6.4 CASE REPORT FORM AND PATIENT NUMBERS

Case Report Forms (CRFs) will be used to collect data at enrolment to this study. Patient numbers will be assigned a 2-digit site code and a 3-digit patient number sequentially beginning with 001.

#### 6.5 SPECIMENS AND LABORATORY HANDLING

All samples will be analysed at Imperial College Healthcare NHS Trust laboratories (operating as North West London Pathology). Research samples will be processed and analysed at the Immunology of Infection lab at Imperial College London, St Mary's Campus.

## 7 TREATMENT

It is accepted that SOC may change during a rapidly evolving pandemic. Co-enrolment to other trials and rescue therapy, either pre- or post-randomisation, is permitted and will be accounted for in the statistical analysis.

Table 2. Ruxolitinib (RUX)

Period	Dose	Frequency
Day 1-7	10mg	Twice daily
Day 8-14	5mg	Twice daily

Table 3. Fostamatinib (FOS)

Period	Dose	Frequency
Day 1-7	150mg	Twice daily

MATIS version 4.0 dated 2nd November 2022

IRAS: 282552 Page **32** of **57** 

Day 8-14 100mg Twice daily	
----------------------------	--

#### 7.1 INTERIM ANALYSIS TO GUIDE DOSING REGIMEN

There is no prior evidence with which to base particular dosing regimens for RUX or FOS for the treatment of COVID-19 pneumonia. After the first 10 patients have been recruited in each arm, an interim analysis will therefore be conducted to test whether a mean 25% decrease in CRP (an inflammatory biomarker) has been achieved in each of the treatment arms compared to SOC at day 14. This analysis will inform a recommendation by the DMC to consider dose escalation for subsequent patients. In the event of that the dosing regimen is changed for subsequent patients, all patients will be included in the final analysis of the primary outcome, but a sensitivity analysis will be performed that excludes patients treated with the prior dosing.

#### 7.2 FUTURE CHANGES TO STANDARD OF CARE

The study team will remain cognisant of the prevailing global literature during the current pandemic on effective therapies for COVID-19 pneumonia. If a treatment emerges with efficacy and safety profile that is superior to SOC then options for adoption of the new therapy as SOC will be discussed with the DMC. Specifically, the impact that the new SOC might have on original trial statistical parameters and outcomes measures will be considered.

